7.3 Adverse Events and Serious Adverse Events

An **adverse event (AE)** is any untoward medical occurrence in a subject during participation in the clinical study or with use of the experimental agent being studied. An adverse finding can include a sign, symptom, abnormal assessment (laboratory test value, vital signs, electrocardiogram finding, etc.), or any combination of these regardless of relationship to participation in the study.

A serious adverse event (SAE) is one that meets one or more of the following criteria:

- Results in death
- Is life-threatening (places the subject at immediate risk of death from the event as it occurred)
- Results in inpatient hospitalization or prolongation of existing hospitalization
- Results in a persistent or significant disability or incapacity
- Results in a congenital anomaly or birth defect

An important medical event that may not result in death, be life threatening, or require hospitalization may be considered an SAE when, based upon appropriate medical judgment, the event may jeopardize the subject and may require medical or surgical intervention to prevent one of the outcomes listed in this definition.

During each study visit, participants will be asked to report any potential side effects and the SAFTEE score will be reviewed by a clinician. Abnormal blood panels and ECGs will be monitored by a clinician and repeated as needed. In addition, participants will be asked the general question "Has anything else felt different since

you started the study medication?" in order to capture unknown side effects or AEs. A clinician will meet with a study participant at each visit and document the occurrence of any potential side effects. The side effects will be classified using the Adverse Event grading scale as outlined in the DSMP. All AEs will be documented in both the participant chart and the REDCap data capture system.

An SAE can also meet criteria for an **Unanticipated Problem (UP)**. The Office for Human Research Protections (OHRP) considers unanticipated problems involving risks to subjects or others to include, in general, any incident, experience, or outcome that meets **all** of the following criteria:

- Unexpected in terms of nature, severity, or frequency given (a) the research procedures that are described in the protocol-related documents, such as the IRB-approved research protocol and informed consent document; and (b) the characteristics of the subject population being studied;
- Related or possibly related to participation in the research ("possibly related" means there is a reasonable possibility that the incident, experience, or outcome may have been caused by the procedures involved in the research); and
- Suggests that the research places subjects or others at a greater risk of harm (including physical, psychological, economic, or social harm) than was previously known or recognized.

Any SAE, including death to any cause, will be reported to the UT Southwestern IRB only if the event is considered an Unanticipated Problem Involving Risks to Subjects or Others (UPIRSO). UT Southwestern IRB reporting policy specifies that only events that are unexpected, and possible/definitely related to the study, and place a subject or other participants at a greater risk (thus meeting criteria for UPIRSO) need to be reported to the IRB. For example, an SAE (including, but not limited to, a death unrelated to the study or the study medication) will not need to be reported to the UT southwestern IRB. It will, however, be reported to the DSMB and NCCIH according to the specified guidelines, and will be reported to the IRB (along with any other AEs) during the annual continuing review. UT Southwestern will reject any reportable events that do not meet criteria for UPIRSO or warrant a substantial protocol change.

Adverse Events (AE) reporting for IND Studies

SAEs that are unanticipated, serious, and possibly related to the study intervention will be reported to the DSMB, IRB, FDA, and NCCIH in accordance with requirements. For the IND:

- 7-day IND Safety Report (unexpected fatal or life-threatening AEs related to the intervention); a copy of the report sent to the FDA will be submitted to the NCCIH Program Officer and DSMB within 24 hours of FDA notification.
- 15-day IND Safety Report (any other serious and unexpected AE related to the intervention); a copy of the report submitted to the FDA will be submitted to the NCCIH Program Officer and DSMB within 24 hours of FDA notification.
- All other AEs documented during the course of the trial will be reported to NCCIH
 on an annual basis by way of inclusion in the annual report and in the annual AE
 summary which will be provided to NCCIH and to the DSMB. The DSMB Report
 will state that all AEs have been reviewed.

Reporting of Pregnancy

All participants will be required to have a negative pregnancy test prior to the study enrollment. In the event of an unexpected pregnancy, the study participation will be discontinued and the appropriate referrals will be provided to the participant. . Participants will be provided with contact information to the UT Southwestern and Parkland Hospital OBGYN clinics, as well as additional local resources as needed. If a participant elects to continue pregnancy, and with participant permission, she will be contacted at 3 month intervals (months 3, 6, and 9) to check the status of pregnancy, as well as at 3 months post-partum to collect information on pregnancy outcome. The pregnancy and the follow-up plan for the participant will be reported to the DSMB and NCCIH within 48 hours of PI awareness. The pregnancy will be reported to the UT Southwestern IRB if it also meets criteria for UPIRSO and requires a modification to the protocol.

7.5 Followup for Adverse Events

The PI will record all reportable events with start dates occurring any time after informed consent is obtained until 7 (for non-serious AEs) or 30 days (for SAEs) after the last day of study participation. At each study visit, the investigator will inquire about the occurrence of AE/SAEs since the last visit. Events will be followed for outcome information until resolution or stabilization. The study clinician, with PI delegation, will make the final determination on whether an AE/SAE is considered resolved.

7.6 Safety Monitoring

The NCCIH requires that all Human Subjects research studies undergo independent monitoring, and NCCIH Program Officials will provide specific guidelines to the PI for the study.

8. INTERVENTION DISCONTINUATION

Study intervention may be discontinued for participants for any of the following reasons:

- Development of any exclusion criteria for the study while participating in the study (e.g., development of severe MDD).
- Development of active suicidal or homicidal ideation with plan and intent, clear and progressive worsening of psychiatric symptoms that in the opinion of the investigator makes continued care within the research study unsafe.
- Development of psychotic features (hallucinations, delusions, disorganized thoughts)
- Development of severe or life-threatening medical condition, pregnancy or psychiatric hospitalization.
- Withdrawal of informed consent by the participant.
- Opinion of the investigator that continued participation is unsafe or unwise.
- Participants who start psychotropic medications during the trial will be withdrawn from the study. Because the study has a short observation period and a crossover design we suggest that this is both a practical and scientifically justified

approach.

Participants will continue to be followed with their permission if study intervention is discontinued. Participants discontinued prior to Visit 6 will be asked to return for a Safety Visit. Participants who meet discontinuation criteria at Visit 6 will return for the regularly scheduled Safety Visit within 14 days of study discontinuation.

At the Safety Visit, assessments will be given based on their clinical relevance to the discontinuation criteria met by the study participant, in addition to a doctor visit, routine vital signs, AE review, and side effects scales. Clinically significant abnormal labs will be repeated at the Safety Visit, if necessary, and participants will continue to be followed until safety concerns are adequately resolved and appropriate referrals have been made.

Study participants may choose, at any time, to stop participating in the study. In the event that a participant chooses to do so, the study intervention will be stopped and the participant will be asked to return for a Safety Visit as outlined above.

Due to the short length of each treatment exposure (7 days), no temporary discontinuations will be allowed. In the event of participant discontinuation, no further evaluations will be performed for outcomes, only the safety measures as indicated above.

9. STATISTICAL CONSIDERATIONS

9.1 General Design Issues

The R61 phase involves a randomized, double-blind, cross-over design of 500 mg/d pregnenolone, 800 mg/d pregnenolone, and placebo for seven days with a 14-day washout between each exposure in 31 women with MDD.

Hypothesis: Pregnenolone is associated with improvement in depressive symptom severity in women that is associated with changes in rsFC and GABA.

Primary Study Aims R61 Phase (biosignature determination):

- Determine if an increase in amygdala-PCC functional connectivity ($d \ge 0.5$) is observed with pregnenolone, as compared to placebo in women with MDD.
- Determine if an increase in dIPFC-insula functional connectivity ($d \ge 0.5$) is observed with pregnenolone, as compared to placebo in women with MDD.
- Determine if an increase in occipital GABA concentration ($d \ge 0.5$) is observed with pregnenolone, as compared to placebo, in women with MDD.

Secondary Study Aims R61 Phase:

- Assess safety and tolerability of pregnenolone at the doses tested.
- Assess bioavailability of pregnenolone by demonstrating increases in serum pregnenolone and allopregnanolone levels with pregnenolone administration.

• Identify a dose of pregnenolone that demonstrates bioavailability, tolerability and that is associated with a significant change in a biosignature.

9.2 Sample Size and Randomization

Data from pooled randomized, controlled trials of how standard depression therapies influence proposed neuroimaging biosignatures (GABA) in a depressed population, and our rsFC connectivity data with pregnenolone, suggest that a sample size of n=31 would allow for > 25% attrition (higher than expected), and provide > 90% power with an α = 0.05 in the R61 phase of the experiment.(22) A sample size of 31 is adequate to detect within-group dose condition differences (500 mg vs. 800 mg vs. placebo) with an effect size (Cohen's d) of about 0.82 (medium to large) in the first phase. Thus, each pregnenolone dose will be compared to placebo separately. The reported d for changes in occipital GABA with depression treatment ranges from 1.28 to 1.59. The rsFC increase with pregnenolone, as compared to placebo, between the amygdala (seed region) and PCC in our pilot had an effect size of d = 3.28.

Randomization will be performed by an independent unblinded statistician (see Study Team Roster) not involved in data analysis prior to recruitment using a random number sequence (Statistical Analysis System [SAS] Proc Plan). A randomization list will be maintained in a password protected folder by an unblinded staff member with no participant contact. See section 6.2.3 Blinding for more information regarding the unblinding procedures.

9.3 Definition of Populations

The intent-to-treat (ITT) sample will be defined as follows: if a participant completes visits with at least one MRI scan, then useable data will be obtained. There is no baseline MRI, but only an MRI after each condition. Thus, having one scan will define ITT. In the case of early dropouts, the last data point collected will be entered into analyses for that participant (e.g. data on one dose condition but not all conditions).

9.4 Interim Analyses and Stopping Rules

No interim analysis is planned for the R61 phase. The analysis will be conducted after the R61 phase is completed to determine whether the trial progresses to the R33 phase.

The DSMB in consultation with NCCIH and the PI may recommend a temporary suspension of enrollment and/or study intervention if pregnenolone is associated with adverse effects that occur with greater than anticipated frequency and severity, and call into question the safety of pregnenolone. If a temporary suspension is recommended, then a complete safety review will be conducted in order to determine whether the study should proceed per protocol, proceed with enhanced monitoring, be further investigated, be discontinued, or be modified and then proceed.

9.5 Outcomes

9.5.1 Primary Outcomes (biosignature determination)

- 1. Amygdala-PCC functional connectivity
- 2. dIPFC-insula functional connectivity

Changes in rsFC using a region of interest (ROI) approach for the following regions 1) amygdala (seed region) and PCC, and 2) dorsolateral PFC (dIPFC, seed region) and insula. ROIs will be anatomically defined using MarsBaR.

3. Occipital GABA concentration

LCModel software(23) will be used to analyze spectra using calculated (model) spectra of 20 metabolites as basis sets, and similar analysis will be conducted for preliminary ¹HMRS studies. Spectral fitting range will be set to 0.5 – 4.2 ppm. We will estimate GABA, and other metabolite, concentrations with respect to brain tissue water concentration (GM+WM) (24, 25), excluding CSF water. GABA and Glu will be measured using MEGA-PRESS difference spectra. NAA, Cr and Cho will be estimated using edit-OFF subscan spectra. GM, WM, and CSF fractions within ¹HMRS voxel will be estimated from T1-weighted images using the Statistical Parametric Mapping software.

9.5.2 Secondary Outcomes

- **4. Tolerability.** Tolerability will be defined as no SAEs related to the study medication and no more than 10% of participants have a moderate or severe AE that is related to the product.
- 5. Bioavailability. Serum pregnenolone and allopregnanolone levels.
- 6. Dose of pregnenolone. Determine pregnenolone dose that demonstrates bioavailability, tolerability and that is associated with a significant change in a biosignature.

9.6 Data Analyses

Primary Aims:

To determine biosignature(s) sensitive to pregnenolone, scores on biosignatures will be compared between conditions using a random regression model with time and dose (500mg, 800mg, placebo) as within-subject factors using the PROC MIXED function. In determining statistical significance, Bonferroni corrections will be made to control for Type I error rates. Additionally, to explore the role neurosteroid levels have in the relationship between dose condition and biosignatures, separate mediational path models will be run. Specifically, following Preacher and Hayes' (2008)(26) bootstrap procedure, 5,000 bootstrap resamples will be examined using the Process macro (Hayes, 2013)(27) for SAS 9.4. In the path model, each biosignature will be regressed separately on to dose condition with neurosteroid levels included as a mediator (indirect effect). The following covariates will be included in this exploratory model: baseline scores on HRSD, age, depression severity, and depression duration.

95% confidence intervals will be examined and if the confidence interval does not contain zero, the effect will be considered statistically significant.

Secondary Aims: Tolerability

Tolerability will be defined as no SAEs related to the study medication and no more than 10% of participants have a moderate or severe AE that is related to the product. For dichotomous outcomes (e.g. drop out vs. completer) PROC NLMIXED will be used where dose and time will be added as within-subject factors and status as a dichotomous outcome variable.

Secondary Aims: Bioavailability

To assess **bioavailability** of pregnenolone and allopregnanolone, mean pregnenolone and allopregnanolone levels in each condition will be compared using a one-way repeated measures ANOVA. PROC ANOVA will be used to examine overall differences for each outcome, Bonferroni corrections will be made to control for Type I error rates, and Tukey's post hoc procedure will be used to examine pairwise comparisons for each condition.

Secondary Aims: Pregnenolone Dose

To identify a dose of pregnenolone that demonstrates bioavailability, tolerability and that is associated with a significant change in a biosignature, a one-way repeated measure multivariate analysis of variance (MANOVA) with dose as a within subject variable and exit biosignature engagement and overall tolerability (as assessed by total SAFTEE scores) as outcome measures will be performed using the MANOVA statement in the PROC GLM function in SAS 9.4.

Additionally, the results from the R61 phase will be used to determine whether the trial progress to the R33 phase. Using the results of these analyses, go/no-go rules will then be applied to determine if the study progresses to the R33 phase. The "go" criteria will be defined as meeting 2 of 3 of the biological signatures, with a medium effect size (defined as Cohen's d \geq 0.5) in the proposed direction.

Go:

At least 2 of 3 biosignatures (amygdala-PCC, dIPFC-insula, occipital GABA concentration) achieve at least a medium effect size (defined as Cohen's d ≥ 0.5) in the proposed direction (increased rsFC with fMRI, increased GABA with MRS). Biomarkers were selected based on their relevance to depression, antidepressant response and postulated pregnenolone (or active metabolite) mechanism(s) of action. A detailed justification of the biosignatures with literature references is provided in the Research Strategy (section 3.3.e.)

- If more than one biosignature achieves the proposed effect size, then the project proceeds to the R33 phase and includes any biosignatures reaching the proposed effect size. Two of three biosignatures need to be in the proposed direction. If one or two of the biosignatures is on the opposite direction of prediction, then this will result in a "no-go" signal.
- The dose (500 mg/d or 800 mg/d) with a go on biosignature must show adequate tolerability. Tolerability will be defined as no SAEs related to the study medication and no more than 10% of participants have a moderate or severe AE that is related to the product.
- If both doses of pregnenolone achieve the go threshold, including having adequate tolerability, (on either the same or different biosignature) then the dose with the largest effect size on a biosignature (defined using Cohen's d) on a biosignature will be selected for the R33 phase.

No-go:

- None of the go rules are achieved.
- A biomarker(s) achieves proposed effect size, but in the opposite direction of prediction.
- A biomarker(s) achieves proposed effect size, but tolerability is not adequate as judged by PI and DSMB. Tolerability will be defined as no SAEs related to the study medication and no more than 10% of participants have a moderate or severe AE that is related to the product.

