Participants meeting the required inclusion criteria and none of the exclusion criteria, as determined by the PI or study clinician, will be randomized into the study. Any participants who sign a consent will be noted in the "Enrollment Log". If a participant is determined to be ineligible for the study post-consent, they will be considered a "screen fail" and an appropriate note will be made in the log.

Randomization will be performed by a statistician using a random number sequence (SAS Proc Plan). A randomization list will be maintained in a password protected folder by an unblinded staff member with no participant contact. In the R61 phase, a crossover design will be used so each participant will receive each of three study drug conditions in a random order. All tests will be 2-sided with p< 0.05 to assess significance.

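### Section 9.6 applies Bonferroni to an undefined family of primary tests; Holm's procedure would hold the same familywise error and never reject less, an optional gain of about 0 to 10 points of power per test at the design effect

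*Combined protocol and SAP*

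**What the plan says.** Section 9.6 (Primary Aims) compares biosignature scores between the three conditions in a mixed model and adds: "In determining statistical significance, Bonferroni corrections will be made to control for Type I error rates". No stepwise procedure is named and the number of tests is not given. Section 4.3 sets the level: "All tests will be 2-sided with p< 0.05 to assess significance".

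The plan has three primary biosignatures (section 9.5.1): amygdala-PCC connectivity, dlPFC-insula connectivity and occipital GABA. Section 9.2 adds: "Thus, each pregnenolone dose will be compared to placebo separately". Two dose contrasts on three biosignatures make six tests.

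The same section says that 31 women allow for more than 25% attrition and "provide > 90% power with an α = 0.05 in the R61 phase of the experiment", and that this number detects differences "with an effect size (Cohen's d) of about 0.82 (medium to large) in the first phase".

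Significance is used again in secondary outcome 6 (section 9.5.2), which seeks a dose showing bioavailability, "tolerability and that is associated with a significant change in a biosignature". Section 9.6 analyses that outcome by a repeated-measures MANOVA. The go/no-go rule and the choice between doses, also in section 9.6, rest on an observed Cohen's d of at least 0.5 and on tolerability, with no p-value.

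**The concern.** Bonferroni holds every test in the family to 0.05 divided by the family size. Holm does so only for the smallest p-value and then relaxes the threshold step by step, with the same familywise guarantee under any correlation. For reject-or-not decisions on a fixed family, Bonferroni therefore has no advantage.

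The trial hopes that several biosignatures respond, perhaps at both doses, and that is where Holm gains most. At stake is how many individual biosignature-by-dose effects can be declared significant. Because the family is undefined, the threshold itself is also open: 0.05/3 = 0.0167 or 0.05/6 = 0.0083.

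**Working it through.** **Inputs.** From section 9.2: 31 women, 25% attrition, d = 0.82. From section 4.3: two-sided 0.05. From sections 9.5.1 and 9.2: three biosignatures and two dose contrasts. Assumed: d is the mean paired difference divided by its standard deviation, a paired t test stands in for the mixed-model contrast, real effects are equal in size, and correlation between biosignatures is 0 to 0.5.

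**1. The plan's own figure.** Evaluable women: 31 × 0.75 = 23.25, so 23. Power is P(|T| > t(1 − α/2, n − 1)), where T is noncentral t with n − 1 degrees of freedom and noncentrality d√n = 0.82 × √23 = 3.93.

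| Level per test | Critical t (22 df) | Power |
|---|---|---|
| 0.05 | 2.07 | 96.4% |
| 0.05/3 | 2.59 | 89.9% |
| 0.05/6 | 2.90 | 83.6% |

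The effect detectable with 90% power at 0.05/3 and n = 23 is d = 0.821. So the stated 0.82 reproduces, and it is consistent with a three-test Bonferroni correction. Six tests would fall short of the stated power.

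**2. The two rules.** Bonferroni rejects when p ≤ 0.05/m. Holm orders the p-values and rejects the k-th smallest while every p(j) ≤ 0.05/(m − j + 1) for j up to k. For m = 6 the thresholds are 0.0083, 0.0100, 0.0125, 0.0167, 0.0250 and 0.0500. The first equals Bonferroni's, so the chance of at least one rejection is identical.

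**3. Six tests** (simulated paired t tests, 15,000 to 30,000 trials per scenario; the two dose contrasts share the placebo scan unless noted). Power per test for the real effects:

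| Women, d | Real effects | Bonferroni | Holm | Gain (points) |
|---|---|---|---|---|
| 23, 0.82 | all six, biosignatures independent | 83.6% | 94.5% | 10.9 |
| 23, 0.82 | all six, biosignature correlation 0.5 | 83.7% | 93.2% | 9.5 |
| 23, 0.82 | two biosignatures, both doses | 83.6% | 88.8% | 5.2 |
| 23, 0.82 | one dose, all three biosignatures | 84% | 87% | 3 |
| 23, 0.82 | one biosignature, both doses | 83.5% | 84.9% | 1.4 |
| 31, 0.82 | all six | 95.1% | 99.1% | 4.0 |
| 31, 0.5 | all six (all tests correlated 0.5) | 49% | 60% | 11 |
| 31, 0.5 | two of six (all tests correlated 0.5) | 49% | 51% | 1.4 |

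With independent biosignatures, the all-six case at 31 women and d = 0.5 is 49.2% against 60.8%, a gain of 11.6. Under the global null the two methods had the same familywise error, between 4.6% and 4.9% across runs. In the d = 0.82, 23-women, all-six case with independent biosignatures, the chance that all six are significant rises from 39% to 80%.

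**4. Three tests** (60,000 trials). At 23 women and d = 0.82, power per test goes from 90% to 95–96% with all three effects real, to about 92.5% with two, and rises 0.1 point with one. At 31 women it goes from 97.4% to 99.1–99.3% with all three real. At d = 0.5 with all three real, it goes from 44% to 52% (23 women) and from 60% to 69–70% (31 women).

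**5. Larger effects.** Section 9.2 says: "The reported d for changes in occipital GABA with depression treatment ranges from 1.28 to 1.59". It also cites 3.28 for amygdala-PCC connectivity. At d = 1.28, 23 women and 0.05/6, single-test power is already 99.9%, so nothing is left to gain.

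**6. Intermediate effects.** The documents name no effect between 0.5 and 0.82, but gains there can be larger. With six real effects, d = 0.65 and 31 women, power goes from 77.8% to 90.0%. The largest gain found was about 15 points, at d = 0.7 with 23 women and uncorrelated tests.

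**The case against.** Bonferroni is a valid, prespecified, conservative choice for a phase I biomarker trial, and it gives simple simultaneous confidence intervals that Holm does not match. That stands, although section 9.6 promises no simultaneous intervals for the primary contrasts; its 95% intervals belong to the mediation model.

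The sample size fits a family of three better than six. That stands too, and it matters for the comparison. Holm never rejects less on the same family, but Holm on six tests against Bonferroni on three is not a pure gain. At 23 women and d = 0.82, Bonferroni on three gives 89.9%. Holm on six gives 94.5% with all effects real and biosignatures independent, 88.8% with two biosignatures active and about 87% with one active dose. On the other side, three tests within each dose, each set held at 0.05, would bound the error over both doses only at 2 × 0.05 = 0.10. The documents do not settle which family is meant.

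A reader might infer that the plan loses about 10 points of power on every test for nothing. The documents do not support this: that size at the design effect needs six tests with all six effects real. A reader might also infer that the decision to proceed, or the chance of finding any responsive biosignature, is at risk. It is not. Go/no-go and dose selection use observed d, and the first Holm threshold is Bonferroni's.

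**Conclusion.** The point holds as an optional efficiency improvement, not as an error in the plan. Section 9.6 leaves the family undefined and uses a procedure that Holm matches or beats for rejection decisions on any fixed family.

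At d = 0.82 with 23 women, the gain per test is up to about 10 points with six tests all real, falling to about 5, 3 and 1 as fewer effects are real. It is 5 to 6 at most with three tests. At d = 0.5 with 31 women and six tests it is about 1 to 11 points, and at the effects cited in section 9.2 it is about zero.

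The benefit is in how many biosignature-by-dose effects can be declared significant. For outcome 6, which needs only one biosignature, it would matter mainly when a second significant result is needed, for example if the first significant dose fails on tolerability. The figures rest on d being the standardised within-woman difference, equal real effects, and correlations of 0 to 0.5, none of which the documents state.

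**What to change.** In section 9.6, replace the Bonferroni sentence for the primary aims with:

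> The primary dose-versus-placebo tests (three biosignatures × two doses) form one family of six, controlled at two-sided 0.05 by the Holm step-down procedure; adjusted p-values are reported.

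State that the significant change required by outcome 6 is read from these adjusted p-values, and reconcile this with the MANOVA that section 9.6 now assigns to that outcome. If the sponsor intends a family of three, say so and say how error is controlled over the two doses; Holm applies in the same way.

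The cost is a few sentences, with no change to data, sample size or familywise error level. Holm has no equally simple simultaneous confidence intervals, so Bonferroni intervals may be tabulated alongside if wanted.

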Further evidence of the safety and tolerability of pregnenolone comes from a study of 120 patients (n=38 women) with schizophrenia receiving 500 mg of pregnenolone or placebo for eight weeks.(3) The number of participants experiencing treatment-emergent adverse events was comparable between the placebo and pregnenolone groups (58% vs. 55%, respectively). Moderate-intensity adverse events were reported by 8.3% of participants in the placebo group and 13.3% of participants in the pregnenolone group. No participants in either group reported adverse events of severe intensity. Three participants in the pregnenolone group and none in the placebo group had serious adverse events (SAEs); no SAEs were related to pregnenolone. Study medication was discontinued in only one participant (secondary to reasons unrelated to study drug).

Studies of pregnenolone for arthritis from the 1950s provide longer-term and higher-dose safety data. McGavack gave pregnenolone with doses ranging from 400-1000 mg/day for a duration, in some cases, longer than one year with good safety and

tolerability.(19) Freeman et. al. also gave pregnenolone doses of 700-800 mg/day for up to 30 weeks with good tolerability.(20)

As mentioned above, pregnenolone appears to increase levels of progesterone. Marx et al. reported a mean increase in progesterone from 0.38±0.15 ng/ml to 2.17±0.64 ng/ml in patients with schizophrenia given pregnenolone for eight weeks at the dose proposed in the current application.(3) Eight of these nine participants were men. Thus, the impact of pregnenolone on progesterone in women is not well studied. The mean progesterone level achieved during pregnenolone administration in this study was higher than is typical for men (0.3-1.2 ng/ml), postmenopausal women (<0.7 ng/ml), or premenopausal women during the follicular phase (0.2-1.2 ng/ml), but was lower than during the luteal phase (3.3-25.0 mg/ml). Oral contraceptives containing the combination of progestin (a synthetic progesterone) AND estradiol were shown in the Women's Health Initiative, following several years of treatment, to increase the risk of deep vein thrombosis, pulmonary embolism, myocardial infarction, breast cancer, and dementia in postmenopausal women.(21) Therefore, this study excludes persons at an elevated risk, based on personal, and also excludes women over 65 years of age.

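### The bioavailability test is a one-way PROC ANOVA that does not fit the plan's own rule for partial data and, on untransformed levels, could lose power for dose versus placebo

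*Combined protocol and SAP*

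**What the plan says.** For serum pregnenolone and allopregnanolone, Section 9.6 (Secondary Aims: Bioavailability) states that "mean pregnenolone and allopregnanolone levels in each condition will be compared using a one-way repeated measures ANOVA" and that "PROC ANOVA will be used to examine overall differences for each outcome". It adds a Bonferroni correction, and "Tukey's post hoc procedure will be used to examine pairwise comparisons for each condition". It names no period factor, no transformation and no rule for missing samples.

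The primary aims in the same section use a "random regression model with time and dose (500mg, 800mg, placebo) as within-subject factors using the PROC MIXED function". The serum samples and the scans come from the same visits (2, 4 and 6; Section 6.1).

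Section 9.3 keeps a dropout's data even when only one dose condition was observed. Section 8 stops outcome collection at discontinuation, so incomplete records will occur if anyone leaves early. Section 9.2 states that "a sample size of n=31 would allow for > 25% attrition (higher than expected), and provide > 90% power".

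Section 1.2 defines bioavailability as a rise in the two serum levels with pregnenolone. Section 9.5.2 makes it one element of the dose objective: "Determine pregnenolone dose that demonstrates bioavailability, tolerability" and a biosignature change.

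**The concern.** Three features of the planned test sit badly with the rest of the plan.

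- **Partial data.** A one-way repeated measures ANOVA in PROC ANOVA assumes every woman supplies all three conditions. Section 9.3 says otherwise.
- **Period.** The primary model carries a time factor. This one, for samples taken at the same visits, does not.
- **Scale.** Nothing says that levels will be logged. If they are not, ANOVA and Tukey use one error variance for all three conditions. When spread rises with level, the 800 mg/d condition inflates the error used to compare 500 mg/d with placebo.

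At stake is whether a real rise over placebo is detected. That contrast defines bioavailability and so feeds the dose objective.

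**Working it through.** **1. The plan's own figure.** Allowing 25% attrition, 23 / 0.75 = 30.7, so 31 women give about 23 completers. The level is set by "All tests will be 2-sided with p< 0.05 to assess significance". A paired t-test at d = 0.82 with n = 23 has 96.4% power at 0.05, and 89.9% at 0.05/3. The stated power therefore reproduces. It was set for the biosignatures; none is stated for bioavailability.

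**2. The only steroid spread in the documents.** Section 7.2 reports "a mean increase in progesterone from 0.38±0.15 ng/ml to 2.17±0.64 ng/ml". The mean rises 2.17/0.38 = 5.7-fold and the ± figure 0.64/0.15 = 4.3-fold. Spread growing with level points towards a log scale, but this is a different steroid.

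**3. Assumed inputs (not in the documents).** Lognormal levels; between-woman log SD 0.5; within-woman log SD 0.3, 0.5 or 0.7; 800:500 ratio 1.6; 500:placebo ratio 2, 3 or 6; no period effect; Tukey at 0.05.

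**4. Hand check of the mechanism: two-fold rise, within-woman log SD 0.5, 23 complete women.** Relative levels r are 1, 2 and 3.2. On the raw scale

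Var(Yi − Yj) = (ri² + rj²)·e^1.0 − 2·ri·rj·e^0.75 − (ri − rj)²·e^0.5.

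- Placebo and 500: 5 × 2.718 − 4 × 2.117 − 1 × 1.649 = 3.47
- Placebo and 800: 11.24 × 2.718 − 6.4 × 2.117 − 4.84 × 1.649 = 9.02
- 500 and 800: 14.24 × 2.718 − 12.8 × 2.117 − 1.44 × 1.649 = 9.24

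Pooled mean square = (3.47 + 9.02 + 9.24)/6 = 3.62. SE of a difference = √(2 × 3.62/23) = 0.561. Mean difference, 500 minus placebo = (2 − 1) × e^0.25 = 1.284. Ratio = 1.284/0.561 = 2.29.

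The Tukey threshold with (23 − 1)(3 − 1) = 44 df is 3.43/√2 = 2.43, so the expected statistic falls short of it.

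- With that pair's own variance: SE = √(3.47/23) = 0.389, ratio 3.30.
- On the log scale: SE = 0.5 × √(2/23) = 0.147, ratio 0.693/0.147 = 4.7.
- For 800 versus placebo, raw scale: (2.2 × 1.284)/0.561 = 5.03, well clear of the threshold.

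The loss therefore falls mainly on the lower dose. These are normal approximations; raw levels are skewed, so simulation is the better guide to power.

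**5. Simulated power, 500 mg/d versus placebo, raw against log, 23 complete women on both sides (scale alone):**

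| 500:placebo ratio | log SD 0.3 | log SD 0.5 | log SD 0.7 |
|---|---|---|---|
| 2 | 94% v 100% | 53% v 99% | 23% v 83% |
| 3 | 99% v 100% | 85% v 100% | 52% v 100% |
| 6 | 100% v 100% | 96% v 100% | 77% v 100% |

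**6. Full comparison: 31 women, 8 with only one or two periods.** Planned test (raw, complete cases, no period) against log levels with all available samples and period:

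- two-fold: 23–93% against 86–100%
- three-fold: 52–99% against about 100%
- six-fold: 75–100% against about 100%

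A separate run at log SD 0.5 gave 55% against 99% for a doubling and 87% against 100% for a tripling. Differences of a point or two between runs are simulation error.

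**7. Where the gain arises.** Mostly from the scale. Partial data add a few points (83% to about 86% for a doubling at log SD 0.7). The three steps were separated for 800 versus 500 at ratio 1.6, log SD 0.5 and a six-fold rise at 500: scale +10 points, partial data +5, period −0.5. The period term is worth about +11 to +12 points only if levels drift by 0.6 log units over the periods.

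**The case against.** Much of the opposing case stands.

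- **Dose choice.** A reader might infer that the test weakens the 500 versus 800 mg/d serum comparison and so the choice of dose. The documents do not support this. In Section 9.6 the dose MANOVA takes biosignatures and SAFTEE as outcomes, the tie-break is the largest biosignature effect size, and go/no-go uses biosignatures and tolerability. Bioavailability requires a rise with drug, not a difference between doses.
- **Dropping women.** A reader might also infer that a woman who misses a course is certain to be excluded. That is an inference about how the procedure would be coded; Section 9.3 says that her data are entered. What can be said is that Sections 9.3 and 9.6 do not fit together. Section 9.3 is also framed around scans, so its application to serum should be stated.
- **Raw scale.** This is read from silence; the text speaks only of mean levels.
- **Progesterone figures.** They come from nine patients with schizophrenia, eight of them men, and ± is not defined. Read as SDs, the CV falls from 0.15/0.38 = 39% to 0.64/2.17 = 29%, the mild end of the problem.
- **Large effects.** Section 2.2 reports large neurosteroid increases after a single 400 mg dose. With a six-fold rise and log SD of 0.5 or less, little is lost. The documents give no size for allopregnanolone, however, so this cannot be relied on for both analytes.
- **Attrition.** Section 9.2 calls the 25% margin higher than expected, so the partial-data gain may be smaller.
- **Multiplicity.** Tukey for pairs and Bonferroni across outcomes is the natural reading, so any ambiguity is slight.

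**Conclusion.** The point holds as a minor, secondary-endpoint improvement. The text settles two things: the planned test is a one-way, balanced-data method that conflicts with Section 9.3, and it is a weaker model than the one used for the primary aims.

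The power loss is conditional on untransformed analysis and on assumed variances and ratios. For 500 mg/d versus placebo it ranges from nothing (large rise, low variability) to about 60 points (a doubling at log SD 0.7: 23% against 83–86%). Sample size, dose-selection rule and go/no-go are unaffected.

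**What to change.** Replace the PROC ANOVA text in Section 9.6 with the following:

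- Analyse log serum levels of each analyte in PROC MIXED, with condition and period as fixed effects and woman as a random effect, using all available samples. State that Section 9.3 applies to serum in this sense.
- Prespecify the geometric mean ratios of 500 mg/d and 800 mg/d to placebo, with confidence intervals, as the bioavailability contrasts. Report 800 versus 500 as supportive.
- Use Tukey for the three pairs within an analyte and Bonferroni across the two analytes.

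The cost is SAP wording only. Results are read as ratios instead of differences. No visit, sample or participant is added.
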